2.4.4. Special notes on response assessment

When nodal disease is included in the sum of target lesions and the nodes decrease to 'normal' size (<10 mm), they may still have a measurement reported on scans. This measurement should be recorded even though the nodes are normal in order not to overstate progression should it be based on increase in size of the nodes. As noted earlier, this means that patients with CR may not have a total sum of 'zero' on the case report form (CRF).

In trials where confirmation of response is required, repeated 'NE' time point assessments may complicate best response determination. The analysis plan for the trial must address how missing data/assessments will be addressed in determination of response and progression. For example, in most trials it is reasonable to consider a patient with time point responses of PR-NE-PR as a confirmed response.

Patients with a global deterioration of health status requiring discontinuation of treatment without objective evidence of disease progression at that time should be reported as 'symptomatic deterioration'. Every effort should be made to document objective progression

even after discontinuation of treatment. Symptomatic deterioration is not a descriptor of an objective response: it is a reason for stopping study therapy. The objective response status of such patients is to be determined by evaluation of target and non-target disease as shown in Tables 1 to 3.

Conditions that define 'early progression, early death and inevaluability' are study specific and should be clearly described in each protocol (depending on treatment duration, treatment periodicity).

In some circumstances it may be difficult to distinguish residual disease from normal tissue. When the evaluation of complete response depends upon this determination, it is recommended that the residual lesion be investigated (fine needle aspirate/biopsy) before assigning a status of complete response. FDG-PET may be used to upgrade a response to a CR in a manner similar to a biopsy in cases where a residual radiographic abnormality is thought to represent fibrosis or scarring. The use of FDG-PET in this circumstance should be prospectively described in the protocol and supported by disease specific medical literature for the indication. However, it must be acknowledged that both approaches may lead to false positive CR due to limitations of FDG-PET and biopsy resolution/sensitivity.

For equivocal findings of progression (e.g. very small and uncertain new lesions; cystic changes or necrosis in existing lesions), treatment may continue until the next scheduled assessment. If at the next scheduled assessment, progression is confirmed, the date of progression should be the earlier date when progression was suspected.

2.6.2. Duration of overall response

The duration of overall response is measured from the time measurement criteria are first met for CR/PR (whichever is first recorded) until the first date that recurrent or progressive disease is objectively documented (taking as reference for progressive disease the smallest measurements recorded on study).

The duration of overall complete response is measured from the time measurement criteria are first met for CR until the first date that recurrent disease is objectively documented.

2.6.3. Duration of stable disease

Stable disease is measured from the start of the treatment (in randomised trials, from date of randomisation) until the criteria for progression are met, taking as reference the smallest sum on study (if the baseline sum is the smallest, this is the reference for calculation of PD).

16.4

NEW YORK HEART ASSOCIATION (NYHA) SCALE

Class I – patients with cardiac disease but without resulting limitation of physical activity; ordinary physical activity does not cause undue dyspnoea (or fatigue, palpitation or anginal pain)

Class II – patients with cardiac disease resulting in slight limitation of physical activity; they are comfortable at rest; ordinary physical activity results in dyspnoea (or fatigue, palpitation or anginal pain)

Class III – patients with cardiac disease resulting in marked limitations of physical activity; they are comfortable at rest; less than ordinary physical activity causes dyspnoea (or fatigue, palpitation or anginal pain)

Class IV – patients with cardiac disease resulting in inability to carry out physical activity without discomfort; symptoms of dyspnoea (or of angina) may be present even at rest; if any physical activity is undertaken, discomfort is increased.

16.5 MANAGEMENT OF SKIN TOXICITY

Dermatological toxicity is anticipated for both vandetanib and selumetinib therefore the following guidance is recommended for patients on study and also guidance once study treatment has been discontinued. It is strongly recommended that all patients follow a program of sun protective measures while receiving study therapy and for 3-4 weeks after discontinuing study therapy. The aim is to reduce the risk of development of skin rash, minimize the severity of skin rash, and to minimize the requirement for dose reduction of study therapy. If a patient develops a skin rash, the following actions are recommended for the management of this reaction:

- A variety of agents can be used to manage skin rashes. These include mild to moderate strength steroid creams, either topical or systemic antibiotics, topical or systemic antihistamines, and occasionally retinoid creams. Patients with severe skin rashes, e.g., Stevens-Johnson Syndrome, toxic epidermal necrolysis, erythema multiforme, and toxic skin eruptions, should be treated with systemic glucocorticoids and should not continue treatment, even at a lower dose.
- The rash should be graded/assessed by a physician as soon as possible according to the NCI CTCAE (version 4.02) cutaneous toxicity criteria and documented accordingly
- If the rash is CTCAE Grade 1, consider starting with mild to moderate topical steroids (e.g., betamethasone), topical antibiotics such as clindamycin gel, systemic antibiotics or no treatment if the patient is asymptomatic.
- Please note: Use of topical steroid cream with higher potency may be considered early in patients with moderate rash on the face. Topical or systemic antihistamines, and occasionally retinoid creams can also be considered.
- If a rash of CTCAE Grade 2 or higher is detected, immediate symptomatic treatment should be provided e.g. topical steroid or pimecrolimus cream and consider adding an oral tetracycline or a similar agent.
- If a rash of CTCAE Grade 3 or higher is detected, study treatment must be withheld until recovery to Grade 1 or below (See Section 5.4). The addition of topical steroids is recommended.

Pruritus of any grade may be treated with an antihistamine, such as diphenhydramine or hydroxyzine hydrochloride.

Secondary infection may complicate or worsen skin toxicity. To reduce the likelihood of nasal infection, intranasal mupirocin may be considered. Infected rash may be treated with a short course of an oral tetracycline, such as doxycycline. Sun exposure should be avoided in patients receiving doxycycline or other tetracycline antibiotics.

CONFIDENTIAL

If there is a clinical diagnosis of impetigo, or an infection with *Staphylococcus aureus* is confirmed, topical mupirocin might be used. Infected lesions suspected to be treatment-resistant should be cultured. If there is no improvement after two weeks of treatment, therapy for the rash should be considered ineffective and discontinued and study treatment should not re start.

Xerosis can be treated with classical emollients.

If severe cutaneous toxicity recurs at reduced dose of vandetanib and selumetinib, the patient will permanently discontinue study treatment.

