5.4 Dose modifications

5.4.1 Dose interruptions

In the event of drug related toxicity, drug administration must be withheld (except for skin, fatigue, nausea, myalgia or arthralgia, unless these specific toxicities do not respond to supportive measures) until Grade 1 or below or until the patient meets the eligibility criteria parameters.

- On observation of a Grade 2 cardiac toxicity (any causality), both vandetanib and selumetinib should be stopped until resolution.
- On observation of G3 diarrhoea, if this does not resolve within 48 hours, both vandetanib and selumetinib should be stopped until resolution (i.e. until Grade 0 or 1 or until the patient meets the eligibility criteria parameters).
- On observation of non-specific respiratory signs and symptoms, where infectious, neoplastic, and other causes are unlikely or have been excluded and a diagnosis of interstitial lung disease (ILD) is likely or confirmed, both IMPs should be interrupted.

Patients must meet eligibility criteria parameters prior to each cycle and following a treatment interruption if the intention is to re-treat.

The maximum unscheduled dose interruption period is two weeks. Patients failing to recover to NCI CTCAE Grade 1 or less after two weeks will be withdrawn from the study.

There are overlapping toxicities associated with both vandetanib and selumetinib. Therefore it may not be clear which agent is responsible for any observed toxicity. If this is the case then administration of both drugs must be stopped at the same time until resolution to the above criteria.

Vandetanib administration should not be interrupted if possible; the aim is to maintain vandetanib to reduce the requirement to repeat the 'loading' phase of vandetanib administration. Therefore on observation of a Grade 2 drug related toxicity, selumetinib alone can be stopped (vandetanib can continue as a single agent administration). The patient should be closely monitored (whilst on vandetanib alone) to ensure the toxicity resolves to Grade 1 or less within 24 hours. If toxicity continues at same grade or increases within 24 hours then vandetanib should also be stopped.

To note: selumetinib should not be given as a single agent.

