5.1.1.1.3 Guidelines for management of other toxicities

Guidelines for the management of other toxicity observed during the study can be found in the following appendices:

- Skin toxicity (Appendix 5)
- QTc prolongation (Appendix 6). Please also see Appendix 8 for medications known to prolong QTc.

Electrolyte supplementation with regular laboratory monitoring should be used, when appropriate, to maintain electrolytes within normal limits and to prevent an increased risk of QTc prolongation.

Please also see Appendix 8 for medications with high risk of causing Torsade de Pointes (TdP). This appendix also notes guidance for wash out periods and guidelines for acceptable concomitant medications that may be associated with TdP.

- LVEF drop (Appendix 7). This appendix describes suggested investigation and management of asymptomatic decreases in LVEF).
- Hypertension Should be managed according to local trust policy.

Anticipated vandetanib and selumetinib toxicity

Please see the current versions of the vandetanib and selumetinib IBs and the vandetanib and selumetinib IB supplement for anticipated toxicities and toxicities that have been observed in previous clinical trials.

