5.4.2 Dose reductions

This section is applicable to both the dose escalation phase and also the expansion cohort.

The dose of the combination treatment will be reduced to the previous dose level for any patient who experiences a DLT. If a patient has a dose reduction, their dose should not be re-escalated. NCI CTCAE Version 4.02 is applicable for Section 5.4.2.

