5.4.2.1 Vandetanib and Selumetinib dose reduction

During single agent (vandetanib) phase

If vandetanib administration is interrupted during the single agent phase at the start of Cycle 1 (first 14 days):

- If the interruption was unrelated to vandetanib, administration can recommence as per protocol with no dose reduction.
- If the interruption was related to vandetanib,
 - If toxicity \leq G2, administration can continue as per protocol with no dose reduction on return to Grade 1 or baseline.
 - If toxicity is Grade 3 or above the patient must permanently discontinue study treatment.

During combination phase

If combination treatment is interrupted for **<10 days** during the combination treatment, on re-starting treatment:

- If the interruption was **unrelated to vandetanib or selumetinib**, both drugs can be administered together in combination following the interruption with no dose reduction.
- If the interruption was **related to vandetanib**, on return to Grade 1 or below, vandetanib should be dose reduced to the next lowest dose level od*. A dose reduction to selumetinib is not mandated.

*If single agent dose is 100mg then administration of vandetanib given every other day can be considered however selumetinib must also be administered in combination (selumetinib is not to be administered as a single agent).

- If the interruption was related to selumetinib, on return to Grade 1 or below, selumetinib should be dose reduced to next lowest dose level. A dose reduction to vandetanib is not mandated.

If combination treatment is interrupted for 10-14 days, on re-starting treatment:

- If the interruption was unrelated to vandetanib or selumetinib, vandetanib should be administered as a single agent (no dose reduction) for 10 days at steady state dose level (dependant on cohort) before re-introducing selumetinib (no dose reduction).
- If the interruption was related to vandetanib, vandetanib should be administered as a single agent for 10 days at the next lowest dose level od* before re-introducing selumetinib. A dose reduction to selumetinib is not mandated.
*If single agent dose is 100mg then administration of vandetanib given every other day can be considered however following re-loading, selumetinib must also be administered in combination with vandetanib every other day (selumetinib is not to be administered as a single agent).

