- If the interruption was related to selumetinib, vandetanib should be administered as a single agent for 10 days at the same dose level od (no dose reduction) before re-introducing selumetinib at the next lowest dose level.

Administration of vandetanib given every other day can be considered following a dose interruption however selumetinib must also be administered in combination.

Selumetinib must not be administered as a single agent.

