5.4.2.2 Selumetinib dose reduction

Modification	Selumetinib original dose (at time of dose modification)	Selumetinib reduced dose
1	Original dose (twice daily)	Original dose (once daily) or Reduce by one dose level (twice daily)
2	Original dose (once daily)	Reduce by one dose level (twice daily)
3	Reduced dose level (twice daily)	Reduced dose level (once daily)

Following a dose reduction, the dose will not be escalated again for that patient.

a) Following an initial dose reduction, if a patient experiences an occurrence of a new toxicity requiring treatment interruption, selumetinib should again be withheld until the toxicity improves to CTCAE (version 4.02) Grade 1 or baseline, except for rash where CTCAE Grade 2 rash is acceptable. Upon recovery, treatment may resume as follows:

- The current dose can be reduced to either a once daily administration or
- The dose administered can be at the previous dose level (as investigated in the dose escalation phase) and be administered twice daily (if dose reduction to once daily administration has already taken place).

b) If a patient experiences a recurrence of the same toxicity as that causing a previous dose interruption and/or dose reduction, selumetinib should be withheld until the toxicity improves to CTCAE (version 4.02) Grade 1 or baseline, except for rash where CTCAE Grade 2 rash is acceptable. Upon recovery, treatment should resume at a permanently reduced or adjusted dose:

- 1) Once daily: if no dose reduction has yet occurred
- 2) Reduced dose, twice daily: (if dose reduction to once daily has already occurred)
- 3) Reduced dose, once daily: if steps (1) and (2) have already occurred.

If a patient experiences recurrence of any toxicity requiring dose interruption whilst receiving the lowest dosing schedule for this study, the patient must discontinue study treatment.

If a patient receiving the lowest dosing schedule experiences a novel toxicity that cannot be adequately managed by dose interruption and medical interventions then the patient must discontinue study treatment, as no further dose reductions/adjustments are permitted.

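### Section 5.4.1 exempts skin toxicity from the mandatory hold without a grade limit, while Appendix 16.5 requires a hold as soon as a Grade 3 or higher rash is found

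*Protocol*

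**What the plan says.** Protocol Section 5.4.1 (Dose interruptions) sets the general rule for drug-related toxicity: "drug administration must be withheld (except for skin, fatigue, nausea, myalgia or arthralgia, unless these specific toxicities do not respond to supportive measures". The exemption for skin carries no grade; its only limit is failure of supportive care. The bullets below it add specific holds for Grade 2 cardiac toxicity, Grade 3 diarrhoea that does not settle within 48 hours, and likely or confirmed interstitial lung disease. None concerns rash.

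Appendix 16.5 (Management of skin toxicity) says: "If a rash of CTCAE Grade 3 or higher is detected, study treatment must be withheld until recovery to Grade 1 or below", and refers the reader to Section 5.4.

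The link in the other direction is in the subsection on management of other toxicities within Section 5.4.1.1 (printed as 5.1.1.1.3): "Guidelines for the management of other toxicity observed during the study can be found in the following appendices". Skin toxicity, Appendix 5 (that is, 16.5), is on that list. No text says which rule prevails if they differ.

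**The concern.** Rash is a predicted overlapping toxicity of two drugs being combined for the first time (Section 2.3.4), so whether to dose through a Grade 3 rash is a foreseeable bedside decision at several centres. The two rules have different triggers: detection in Appendix 16.5, failure of supportive care in Section 5.4.1. A site that treats the rash, sees it improve and relies on Section 5.4.1 could carry on dosing through an event for which the appendix requires a hold.

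The difference does not end with the days of the hold. Several later rules in Section 5.4.2 start only once treatment has been interrupted, so two sites facing the same rash could put their patients on different treatment courses.

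**Working it through.** There is no stated figure to reproduce. The check is a comparison of the texts, then of what follows from each.

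**Step 1. The two rules by case (drug-related rash).**

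| Case | Section 5.4.1 | Appendix 16.5 | Agree? |
|---|---|---|---|
| Grade 1-2, responding | No mandatory hold | No hold set by grade | Yes |
| Grade 3 or higher, not responding | Hold | Hold | Yes |
| Grade 3 or higher, responding or response not yet known | No mandatory hold | Hold at detection | **No** |

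Only the last row conflicts.

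**Step 2. Does the cross-referencing settle it?** Section 5.4.1.1 sends the reader to the appendix, but as guidelines. The appendix opens by describing its content as recommended guidance, although the Grade 3 bullet itself is mandatory. Following the appendix's own reference back to Section 5.4 leads to the exemption. Section 5.4.1 also asks that vandetanib be kept going where possible, which leans towards dosing. No order of precedence is given.

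**Step 3. What hangs on whether a hold starts.**

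- *Days 1-14, vandetanib alone.* Section 5.4.2.1 applies if vandetanib is interrupted. For a vandetanib-related interruption: "If toxicity is Grade 3 or above the patient must permanently discontinue study treatment". With no interruption, that rule is not triggered and the patient can go on to the combination.
- *Combination phase, selumetinib-related, hold under 10 days.* "on return to Grade 1 or below, selumetinib should be dose reduced to next lowest dose level". The first step in the Section 5.4.2.2 table is "Original dose (once daily) or Reduce by one dose level (twice daily", and Section 5.4.2 adds: "If a patient has a dose reduction, their dose should not be re-escalated".
- *Combination phase, selumetinib-related, hold of 10-14 days.* In addition, "vandetanib should be administered as a single agent for 10 days at the same dose level od (no dose reduction) before re-introducing selumetinib", and selumetinib then returns at a lower level.
- *Expansion cohort.* Sections 5.7 and 3.1.3 require at least 21 of 28 combination doses in Cycle 1. A 7-day hold inside Days 15-42 leaves 28 - 7 = 21, which passes. An 8-day hold leaves 28 - 8 = 20, so the patient is replaced and not evaluable for response.

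**Step 4. Cost of a hold (illustration only; onset day and hold length are assumed).** Take a selumetinib-related Grade 3 rash found on Day 20, a starting dose of 75 mg bd and a 5-day hold (Days 20-24).

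- Planned Cycle 1 selumetinib: 28 x 150 = 4200 mg. Taken on Days 15-19: 5 x 150 = 750 mg. Remaining days: 25-42, that is 18.
- Restart at 75 mg od: 750 + 18 x 75 = 2100 mg, or 2100/4200 = 50.0%.
- Restart at 50 mg bd: 750 + 18 x 100 = 2550 mg, or 2550/4200 = 60.7%.

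This is the price of following Appendix 16.5. It does not measure the harm of not following it.

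**The case against.** The best defence is that this is a general rule and a specific one. Section 5.4.1 lifts a general hold; it does not tell anyone to keep dosing. Appendix 16.5 then sets the rule for rash, in mandatory words, and each text points to the other. QTc works the same way: its hold threshold is in Appendix 16.6 and is reached through the same list. Severe forms such as Stevens-Johnson syndrome are not to continue treatment in any case. Grade 3 skin events also reach the sponsor as serious adverse events within 24 hours (Sections 9.1 and 9.2), so prolonged unnoticed dosing-through is unlikely.

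Much of this stands. It narrows the conflict to the one case above, and a careful investigator would probably hold. It does not remove the conflict. Section 5.4.1 does not exempt QTc prolongation by name, so the parallel is incomplete. Event reporting does not set the dosing action. The precedence that the defence needs is nowhere stated.

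Three stronger readings are tempting but unsupported.

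- *That escalation or the MTD is affected.* Section 3.1.1 excludes Grade 3 skin toxicity as a DLT while supportive measures are being given. A drug-related interruption beyond 14 days is listed as a DLT, but how that interacts with the skin exclusion is not stated, so nothing is built on it.
- *That the dose losses show the size of the harm.* They arise when treatment is held, and the fix would make them more certain.
- *That the whole skin exemption should stop at Grade 2.* Appendix 16.5 sets the Grade 3 hold for rash only. For pruritus of any grade it suggests an antihistamine and sets no hold.

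**Conclusion.** The inconsistency is real but narrow: a drug-related rash of Grade 3 or higher, responding or not yet shown to be failing on supportive care, at a site that relies on Section 5.4.1. In that case Section 5.4.1 requires no hold and Appendix 16.5 does. The outcome can be permanent discontinuation or continuation in Days 1-14, and a reduced or an unreduced selumetinib dose in the combination phase.

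Its size cannot be put as a rate. The protocol gives no incidence of Grade 3 rash on the combination and no indication of how many sites would dose through, and none is assumed here. The conclusion rests on the wording alone and on the absence of a precedence statement. It is a patient-safety clarification that should be made because it is cheap. It is not a flaw in the statistical design.

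**What to change.** Leave the skin exemption in Section 5.4.1 as it is for other skin events, and add one bullet beside those for cardiac toxicity, diarrhoea and lung disease:

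*Grade 3 or higher rash: withhold study treatment (vandetanib, and selumetinib if in the combination phase) at detection until Grade 1 or below, regardless of response to supportive measures, as in Appendix 16.5.*

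Naming both drugs matters because Section 5.4.1 otherwise prefers to keep vandetanib going.

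The cost is one sentence. The downside is that some patients with a responding Grade 3 rash lose dose intensity, or stop treatment altogether if the rash is vandetanib-related and falls in Days 1-14. Appendix 16.5 read with Section 5.4.2.1 already implies both.

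A separate mismatch can be tidied in the same amendment: for interruptions after an earlier reduction or for a recurring toxicity, Section 5.4.2.2 accepts Grade 2 rash for resuming selumetinib, where Appendix 16.5 asks for Grade 1 or below.

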3.1.1 Definition of dose limiting toxicity

The dose limiting toxicity (DLT) and maximum tolerated dose (MTD) are defined using the National Cancer Institute (NCI) Common Terminology Criteria for Adverse Events (CTCAE) Version 4.02.

During the dose escalation phase, DLTs identified in Cycle 1 of combination treatment will inform the decisions to dose escalate through the increasing dose levels. DLTs will be defined throughout the treatment period during dose escalation and in the expansion cohort and will be considered in determining the RP2D. The criteria by which DLTs will be assessed against during Cycle 1 for dose escalation decisions are as follows:

A DLT is defined as an adverse event considered highly probable or probably related to vandetanib or selumetinib, that occurs during the first cycle of combination period:

- Death
- Neutropenia Grade 4 for ≥ 5 days duration (absolute neutrophil count (ANC) $<0.5 \times 10^9/L$) *

- Febrile neutropenia (fever of unknown origin without clinically or microbiologically documented infection) with Grade 3 or 4 neutropenia (absolute neutrophil count [ANC] $<1.0 \times 10^9/L$ and fever $\geq 38.5^{\circ}\text{C}$);
- Infection (documented clinically or microbiologically) with Grade 3 or 4 neutropenia (ANC $<1.0 \times 10^9/L$)
- Thrombocytopenia Grade 4: a) for ≥ 5 days *See footnote, or b) associated with active bleeding, or c) requiring platelet transfusion.
- Grade 3 or 4 toxicity to organs other than the bone marrow including Grade 3 and Grade 4 biochemical AEs.
- Grade 4 diarrhoea
- Any drug related toxicity that causes a treatment interruption for > 2 weeks (14 successive days). If a patient is deemed fit to restart treatment on Day 15 then this is not a DLT.
- QTc prolongation >500 msec
- Grade 4 hypertension.
- Persistent hypertension (defined as blood pressure $>160/100$ mmHg) sustained for >1 week despite optimal therapy.

EXCLUDING:

- Grade 3 nausea
- Grade 3 or 4 vomiting in patients (who have not received optimal treatment with anti-emetics)
- Grade 3 skin toxicity (and patients are receiving supportive measures to manage toxicity)
- Grade 3 diarrhoea in patients (who have not received optimal treatment with anti diarrhoeals)
- Alopecia (any grade)

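### Section 5.4 and Appendix 16.5 of the protocol give incompatible instructions for repeat or post-reduction rash, on the grade for restarting and on whether recurrence ends treatment

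*Protocol*

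**What the plan says.** Four places in the protocol govern what happens to a patient with rash, and Section 3.1.1 draws on the result.

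- **Section 5.4.1 (dose interruptions).** For drug-related toxicity, "drug administration must be withheld (except for skin, fatigue, nausea, myalgia or arthralgia, unless these specific toxicities do not respond to supportive measures"). The hold ends at Grade 1 or below, or when the eligibility parameters are met. A separate sentence caps the hold: "Patients failing to recover to NCI CTCAE Grade 1 or less after two weeks will be withdrawn from the study". It carries no exception for rash.
- **Section 5.4.2.1.** After a drug-related combination interruption of under 10 days, the responsible drug restarts at a lower level on return to Grade 1 or below, again with no rash exception. After 10 to 14 days, vandetanib is given alone for 10 days before selumetinib returns.
- **Section 5.4.2.2.** Paragraph (a) covers a new toxicity after a first reduction. Paragraph (b) covers recurrence of a toxicity that already caused an interruption or reduction. In both, selumetinib is held until "Grade 1 or baseline, except for rash where CTCAE Grade 2 rash is acceptable". Under (b), "Upon recovery, treatment should resume at a permanently reduced or adjusted dose", in three steps. Recurrence ends treatment only on the lowest dosing schedule.
- **Appendix 16.5 (skin toxicity).** For rash of Grade 3 or higher, "study treatment must be withheld until recovery to Grade 1 or below (See Section 5.4"). Later it says: "If severe cutaneous toxicity recurs at reduced dose of vandetanib and selumetinib, the patient will permanently discontinue study treatment".
- **Section 3.1.1 (DLT definition).** One criterion is "Any drug related toxicity that causes a treatment interruption for > 2 weeks (14 successive days"). A patient judged fit to restart on Day 15 is not a DLT. Grade 3 skin toxicity under supportive measures is excluded from the DLT list.

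**The concern.** Rash is the overlapping toxicity the protocol expects: Section 2.3.4 anticipates more frequent or more intense dermatological events with the combination. Section 5.4.1.1 sends sites to Appendix 16.5 for skin toxicity, and the appendix sends them back to Section 5.4, where they find a different answer. Two sites could each follow the protocol to the letter and treat the same patient differently: one restarts, the other keeps holding or withdraws. Dose intensity, time on treatment and reasons for withdrawal would then depend partly on which page was consulted. Section 5.4.2 applies to both phases, so the expansion cohort is affected as well as the escalation cohorts.

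**Working it through.** No figure in the protocol bears on this point, so the check is a comparison of texts, with two small pieces of arithmetic.

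**1. Restart grade, repeat or post-reduction rash.**

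| Source | Applies to | Grade for restart |
|---|---|---|
| Appendix 16.5 | rash of Grade 3 or higher, study treatment | 1 or below |
| Section 5.4.1, two-week limit | any interruption | 1 or below, else withdrawn |
| Section 5.4.2.1, under 10 days | drug-related interruption of the combination | 1 or below |
| Section 5.4.2.2(a), (b) | selumetinib; new toxicity after reduction, or recurrence | 2 acceptable for rash |

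A recurrent Grade 3 rash that has improved to Grade 2 meets the last row and fails the first. Because selumetinib may not be given alone, a patient whose vandetanib stays held under Appendix 16.5 cannot use the Section 5.4.2.2 allowance at all.

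**2. Recurrence.** Step 1 of Section 5.4.2.2(b) applies where no reduction has yet occurred, so it does not meet the appendix rule. Steps 2 and 3 apply to patients already adjusted, and they resume treatment. Appendix 16.5 discontinues for severe skin toxicity recurring at reduced dose. The two collide for a severe recurrence on reduced dosing before the lowest schedule; at the lowest schedule both end treatment.

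**3. First episode.** Once a first rash has been held, Sections 5.4.1 and 5.4.2.1 and Appendix 16.5 all name Grade 1 or below (Section 5.4.1 adds the eligibility alternative). The mismatch lies in whether a hold begins. Section 5.4.1 exempts skin toxicity unless it fails supportive measures; Appendix 16.5 withholds at Grade 3 or higher without that condition.

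**4. Exposure.** Sections 3.1.3 and 5.7 require at least 21 of 28 combination doses in Cycle 1. In the expansion cohort, a patient below that for any reason is replaced and is not evaluable for response. A hold of 8 days leaves 28 − 8 = 20 doses, which is below 21. Whether a rash is held, and for how long, can therefore decide who is counted.

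**5. Reach into DLT status.** The restart grade matters to the DLT count only if all of these hold: the event falls under Section 5.4.2.2(a) or (b); it arises in the first combination cycle, Days 15 to 42; it is judged probably or highly probably related; and the hold exceeds 14 successive days under one reading but not the other. If a hold of at least 15 days had to finish by Day 42, it would have to start by Day 42 − 15 + 1 = 28. A first rash on the combination, its hold, recovery, restart and recurrence would then have to fit into about Days 15 to 28. The protocol does not say that the hold must finish within the cycle, and an earlier vandetanib-related interruption at Grade 2 or below in Days 1 to 14 could serve as the prior event. The sequence is possible but uncommon.

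**The case against.** The best defence is that the appendix is a specific skin rule that limits a general one, and that its introduction describes it as recommended guidance. This is a plausible reading of the recurrence rules: the appendix speaks of severe skin toxicity at a reduced dose of both drugs, while Section 5.4.2.2(b) is a general selumetinib ladder, and severe is not defined by grade. It is weaker for the restart grade, because the Section 5.4.2.2 exception, "except for rash where CTCAE Grade 2 rash is acceptable", itself names rash. The appendix sentences are also worded as requirements, and no clause gives either text precedence.

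It is also fair to say that the Grade 2 allowance covers selumetinib only, and only repeat or post-reduction events. That stands and limits the point.

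A reader might infer more: that rash DLTs are counted inconsistently as a matter of course, and that one patient with Grade 2 rash at Day 14 of a repeat hold could turn 1 DLT in 6 (escalate) into 2 in 6 (stop). The protocol does not support this, for five reasons.

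- After a 10 to 14 day interruption, Section 5.4.2.1 puts the patient on vandetanib alone for 10 days, so the combination does not simply restart.
- Section 3.1.1 turns on being judged fit to restart, which grade informs but does not settle, and it requires probable or highly probable causality.
- Grade 4 skin toxicity, and Grade 3 without supportive measures, are DLTs whatever the interruption, so a long hold is not shown to be the main route by which rash becomes one.
- Discontinuation is not a DLT criterion, so the recurrence conflict does not enter the count.
- The step from 1 to 2 in 6 presupposes another DLT at that level, and the protocol gives no frequency for the sequence.

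**Conclusion.** The point holds for handling. For repeat or post-reduction rash, the current text gives two incompatible restart grades and two incompatible consequences of recurrence. For first Grade 3 rash under supportive care, it gives two answers on whether to withhold. The main effect is on consistency of treatment, exposure and withdrawal across sites. An effect on DLT status through the restart grade is confined to a repeat hold arising in the first combination cycle and judged probably or highly probably related. The first-episode mismatch decides whether a hold starts, but nothing in the protocol shows how often a rash that is responding would need more than 14 days, so no DLT claim is rested on it.

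The size cannot be quantified, because the protocol states no rate of rash, repeat holds or recurrence for the combination. The conclusion assumes only that both texts are meant to be followed as written and that no document outside the protocol sets precedence. It should be corrected, but it does not by itself undermine the escalation rule.

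**What to change.** Reconcile Sections 5.4.1, 5.4.2.1, 5.4.2.2 and Appendix 16.5 as they apply to rash. In particular:

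- state which text governs when rash is withheld, when each drug may restart, and what follows a recurrence at reduced dose, and make the other places refer to it;
- say what severe means in the recurrence sentence of Appendix 16.5, and whether that sentence requires both drugs to have been reduced;
- say whether the two-week withdrawal limit in Section 5.4.1 uses the same restart condition;
- add to the interruption criterion in Section 3.1.1 that fitness to restart is judged by the governing text.

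The clinical thresholds, including whether first and repeat events share one, are for the sponsor to set; no particular threshold is suggested here. The cost is protocol wording, with no change to sample size, assessments or analysis.
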